#### **8.4. Dose Adjustment Criteria and Dose Escalation Committee (DEC)**

The DEC will be established prior to Screening, the details of which will be set out in a DEC charter.

The DEC will provide recommendations about stopping, modifying or continuing the trial. The DEC will meet for cohort safety review to provide dose escalation recommendations.

Recommendations to escalate/maintain the dose will be made by the DEC in discussion with the PI, and based on a review of available clinical safety and safety laboratory data after completion of 7 days of treatment for each dose escalation cohort. An algorithm regarding progression to cohort expansion will be defined in a DEC charter. Details of the DEC's composition, roles and responsibilities will be described in the DEC charter. The Sponsor will chair the DEC. The DEC charter will include a definition of what safety observations would require a decision about dosing to be made.

## 8.5. Stopping Criteria and Rescue Medication

The Investigator, the study MM (████████), the Sponsor MM or the DEC may decide to stop treatment for an individual subject for meeting the stopping criteria for individual subjects described in [Section 8.5.1](#). Subjects who do not meet individual subject stopping criteria at the clinical evaluation visits will continue dosing until the final day of dosing. Subjects who discontinue study drug will continue to receive safety and efficacy evaluation and all scheduled clinical assessments as well as follow-up.

Due to the naturally progressive nature of the disease, ophthalmic stopping criteria will specifically apply if any subject shows deterioration in their retinal health due to acceleration in the rate of disease, in the opinion of the Investigator. In such an occurrence, if a subject receives rescue medication, they will cease further dosing with study drug, and the last clinical observation will be carried forward for exploratory efficacy analyses. Assessments required for safety endpoints as well as exploratory efficacy will still be performed for any subjects receiving rescue medication, whereas the following assessments that are only required for efficacy endpoints will not:

- DRSS
- Automated Perimetry

The Sponsor MM and/or the DEC may recommend stopping dosing for a cohort or suspend progression to the next higher dose level due to meeting the stopping criteria for a cohort described in [Section 8.5.2](#).

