***Stopping Criteria and Rescue Medication***

The Investigator, the study MM (████████) and also the Sponsor MM and/or the DEC may decide to stop treatment for an individual subject due to an AE, systemic or ophthalmic. Stopping criteria are described in Section 8.5. Due to the naturally progressive nature of the disease, ophthalmic stopping criteria will specifically apply if any subject shows deterioration in their retinal health due to acceleration in the rate of disease, in the opinion of the Investigator. In such an occurrence, if a subject receives rescue medication, they will cease further dosing, be withdrawn from the ██████████ part of the study and the last clinical observation will be carried forward.

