#### **6.4.3. Dose Expansion Cohort**

The highest well-tolerated dose of EXN407 (as determined by the DEC – see [Section 8.4](#)) will be evaluated in a subject expansion cohort consisting of up to a maximum of 40 subjects (randomized to receive EXN407 at the selected dose or vehicle, in a 2:1 ratio). Subjects will receive treatment for 84 days, with 28 days of post-treatment follow-up and an EOS Visit. The DEC will meet to discuss safety and tolerability at intervals to be defined in the DEC charter.

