#### *Analysis and Adaptive Design*

All visit-based data will be analyzed for the study eye at each visit and assessed for any change from baseline. Comparisons with the non-dosed contralateral eye will also be evaluated in each subject. All protocol evaluations will also be completed on the non-dosed contralateral eye. No vehicle-control or other study treatments will be administered to the contralateral eye. The response to active treatment will be compared to vehicle on a group basis (pooling vehicle subjects).

The protocol is adaptive regarding the number and size of cohorts and dose level progression, which will be informed by emergent data and recommendation by the DEC following review of available safety and tolerability data from each cohort. The number of dose levels proposed in this protocol can potentially be reduced or altered based on DEC review and Sponsor decision.

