## 18. STATISTICS

A detailed methodology for the statistical analyses of the data collected in this study will be documented in a statistical analysis plan (SAP), which will be signed off prior to the database lock. All computations will be performed using SAS® version 9.2 (SAS Institute, Cary, NC). Since the primary objective of the study is to evaluate ocular safety and tolerability, no formal hypothesis testing will be performed for any continuous or categorical variables. All statistical analyses will be descriptive in nature and any statistical inference will be carried out according to the analysis plan and interpreted in view of the exploratory nature of the study.

Descriptive statistics (number non-missing values [n], arithmetic mean, SD, 95% confidence interval for mean [where specified], median and range) will be used to summarize continuous variables. Frequencies and percentages will be used to summarize categorical variables. The summaries will be presented by treatment group/cohort and nominal visit/time point (where applicable). Data from the placebo subjects will be pooled (if appropriate).

Baseline demographics and disease characteristics, safety, and [REDACTED] will be summarized descriptively by treatment group and for all subjects combined. Plasma concentrations of EXN407 will be summarized by treatment group and protocol specified time point, and PK parameters calculated where relevant.

Unless stated otherwise, unscheduled data will not be included in the descriptive summaries.

All subject data will be presented in individual subject data listings. Unless otherwise stated, unscheduled visit results will be included in date/time chronological order, within subject listings only. All listings will be sorted by treatment group, subject number, date/time and visit.

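### After rescue, Section 8.5 carries the last observation forward in exploratory efficacy although CMT and BCVA are still measured, and the carried value estimates neither natural target

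*Combined protocol and SAP*

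**What the plan says.** **The rule.** Section 8.5 states that after rescue "the last clinical observation will be carried forward for exploratory efficacy analyses". The synopsis, under Stopping Criteria and Rescue Medication, says "the last clinical observation will be carried forward". There the name of the part of the study that the subject leaves is redacted, and the rule is not visibly limited to efficacy.

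**What is still measured.** Section 8.5 continues: "Assessments required for safety endpoints as well as exploratory efficacy will still be performed for any subjects receiving rescue medication". Two measures that serve efficacy alone, DRSS and automated perimetry, stop at rescue.

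**The same measures elsewhere.** Section 7.2.2 lists the center-subfield measure, macular fluid volume, BCVA and FFA as secondary safety endpoints. Section 18.3.6 summarises observed values and changes from baseline by group, visit and eye, and mentions no carrying forward. It also reports the proportion needing anti-VEGF therapy.

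**The setting.** Section 8.1 compares active treatment with pooled vehicle by group. Section 6.4.3 allows up to 40 expansion subjects at 2:1. Section 18 says "no formal hypothesis testing will be performed for any continuous or categorical variables". Section 8.2 gives the powering of later trials as one use of the efficacy data.

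**What cannot be seen.** Sections 7.1.3, 7.2.4 and 18.4 are redacted, and Section 18 leaves detail to an SAP. The readable text defines no estimand for rescue.

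**The concern.** Section 8.5.3 ties rescue eligibility to a bad CMT or BCVA reading. Section 8.5 does not say which observation is the last one; the natural reading is the last before rescue, which is usually the reading that made the subject eligible. Holding it fixed answers neither of the two questions a later trial team would ask:

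- what the outcome was, rescue included (treatment policy);
- what it would have been without rescue (hypothetical).

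One eye could also have an observed Day 85 value in the Section 18.3.6 tables and a carried value in the efficacy tables. At stake is the group contrast, and with it the effect size used for planning. No confirmatory claim is at stake.

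**Working it through.** The plan gives no effect size, SD or rescue rate for this study, so there is no figure to reproduce. All CMT inputs below are assumptions. Contrasts are EXN407 minus vehicle in µm; negative favours EXN407.

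**1. Where the rule bites.** In the expansion cohort the Schedule of Assessments has SD-OCT on Days 8, 29, 57, 85 and 113. A CMT rise at two consecutive visits cannot be confirmed before Day 29. In the escalation cohorts SD-OCT after dosing falls on Days 8 and 36, and Day 36 is the last visit, so nothing remains to carry forward for CMT. The point concerns mainly the expansion cohort: 40 at 2:1 is about 27 on EXN407 and 13 on vehicle.

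**2. Algebra.** Let pA and pV be the shares rescued on EXN407 and vehicle, L the mean carried change, and T the mean target change in rescued eyes, with L and T equal across arms. Then

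shift = (pA − pV) × (L − T).

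Take L = +85.

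| T | pA 10%, pV 20% | pA 20%, pV 45% |
|---|---|---|
| −50 | −0.10 × 135 = −13.5 | −0.25 × 135 = −33.8 |
| 0 | −0.10 × 85 = −8.5 | −0.25 × 85 = −21.3 |
| +85 | 0 | 0 |
| +150 | −0.10 × (−65) = +6.5 | −0.25 × (−65) = +16.3 |

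The sign turns on the target. With equal shares, and equal gaps in both arms, the shift is zero.

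**3. One eye.** A gap of 65 to 135 µm in one of 13 vehicle eyes moves the vehicle mean by 65/13 = 5.0 to 135/13 = 10.4 µm.

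**4. Simulation against the no-rescue target.** Linear CMT drift, slope SD 25-30 µm per 28 days, reading SD 12 µm, visits on Days 8, 29, 57 and 85. Sizes of the Day 85 difference:

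| Trigger | Vehicle rescued | True | LOCF | Shrinkage |
|---|---|---|---|---|
| 75 µm at two visits | 3-6% | 45.4 | 44.1 | 1.3 (3%) |
| 75 µm at two visits | 3-6% | 45.6 | 41.8 | 3.8 (8%) |
| 75 µm at one reading | 20-29% | 45.7 | 38.8 | 6.9 (15%) |
| 75 µm at one reading | 20-29% | 45.7 | 31.8 | 13.9 (30%) |

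A likelihood repeated-measures analysis of the pre-rescue data gave 45.4-45.7 in all four cases.

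**5. Simulation against both targets.** 27 versus 13 subjects, 6,000-8,000 trials per scenario.

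- *Two-visit rule, 0-9% rescued before Day 85.* LOCF shifts the contrast by 0 to +4 against no rescue and by 0 to −8 against treatment policy. Coverage of the 95% interval is 93-95%.
- *Rescue at the first 75 µm rise.* Inputs: vehicle mean +60, EXN407 mean 0, between-subject SD 60, measurement SD 20, rescue lowers CMT by 100. Rescue reaches 25% of vehicle and 7% of EXN407. The contrast is −52.7 with LOCF, −42.2 as observed and −60.5 without rescue. LOCF overstates benefit by 52.7 − 42.2 = 10.5 against treatment policy and understates it by 60.5 − 52.7 = 7.8 against no rescue. Coverage of the treatment-policy target is 90% with LOCF and 94% with the observed values.
- *Same trigger, both means 0, 7% rescued in each arm.* The shift is −0.1 against no rescue and +0.2 against treatment policy.
- *Looser triggers (first rise of 50 or 30 µm, or a larger rescue effect).* Vehicle rescue runs up to 63%, shifts reach +20.5 and −26.5, and coverage falls to 76% and 64%.

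**The case against.** Several objections have force.

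- **The detailed rule makes rescue rare.** Sections 8.5.1.1 and 8.5.3 require the CMT rise at two consecutive visits. Under step 4's assumptions the Day 85 change has SD √(75² + 2 × 12²) = 77 to √(90² + 2 × 12²) = 92 µm. The standard error is that SD times √(1/27 + 1/13) = 0.338, or about 26 to 31 µm. A shift of 1.3 to 3.8 µm is then about 0.05 to 0.12 standard errors. This stands for CMT-confirmed rescue. However, the synopsis gives a rise above 75 µm with no confirmation, the 15-letter criterion needs none, and the last criterion in 8.5.1.1 rests on Investigator judgement. These passages must be reconciled; until then the rescue rate is uncertain.
- **Observed summaries are already planned.** Section 18.3.6 covers CMT and BCVA as observed, so the post-rescue values are not lost to the report. This stands. They are set aside only in the exploratory efficacy analyses.
- **The study is descriptive**, and Section 18.4, which is redacted, may hold sensitivity analyses. This limits the impact but does not undo the explicit rule in 8.5.
- **The model's recovery in step 4 is largely built in**, because simulated rescue depended only on observed CMT and the arms were very large. This stands, and is why the model should accompany the observed-data analysis.

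A reader might also infer three stronger things.

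- *That LOCF understates uncertainty.* The calculations do not support it. The mean reported LOCF standard error matched the empirical SD of the estimate (20.2 against 20.2; 19.2 against 19.5). It was usually equal to or larger than the standard error from observed post-rescue data (20.2 against 18.6), and smaller only with heavy rescue (17.4 against 19.1). Lost coverage came mainly from bias.
- *That the effect is always diluted, by 15-30%.* Those figures use a single-reading trigger and one target only; against treatment policy the sign reverses.
- *That most vehicle subjects will be rescued*, from the sham figure in Section 6.3 (about 30% free of rescue over six months). That figure comes from other studies in longer-standing disease over a longer period, and the protocol cites it to contrast with subjects identified early.

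**Conclusion.** The point holds, at modest size. For CMT, BCVA and the other shared measures, the exploratory efficacy rule replaces collected values with a selected one that corresponds to neither target. The contrast shifts only when rescue shares, or carried-minus-target gaps, differ by arm. Against the no-rescue target, step 4 puts the shift at about 3-8% under two-visit CMT confirmation; step 5, on other assumptions, puts it at 0 to 4 µm. At 25% versus 7% rescued it is about 8 to 10 µm, in opposite directions for the two targets. These sizes rest on assumed drift, SDs and rescue effect; the direction cannot be fixed until the target is named. The primary ocular adverse-event endpoint is untouched. The change is worth making because the efficacy results are meant to inform later trials and the better data are already being collected.

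**What to change.** In Section 8.5 and the synopsis, replace LOCF as the main rule:

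- State the target for rescue in exploratory efficacy.
- Use the observed post-rescue values where they are collected (treatment policy), in line with Section 18.3.6, and show the share rescued by arm beside them.
- Add a likelihood-based repeated-measures analysis of data up to first rescue (no-rescue target), with baseline, arm, visit and arm-by-visit. Use a simpler covariance if an unstructured one does not fit with about 13 vehicle subjects.
- For DRSS and automated perimetry, use pre-rescue data only.
- Keep LOCF at most as a sensitivity analysis, and define which observation is carried.
- Reconcile the rescue wording in the synopsis with Sections 8.5.1.1 and 8.5.3.

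The cost is a few sentences and a little more analysis, with no new assessments. The model assumes missing at random after rescue. Investigator discretion may strain that, and so may rescue prompted by BCVA when the model holds only CMT. The observed-data contrast includes the effect of rescue therapy and should be read with the rescue shares.

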### 8.5.1. Safety Criteria for Stopping Doses for Individual Subjects

Subjects may withdraw at any time as detailed in [Section 15.1](#). Additionally, if at any time during the study the Investigator determines that a subject's safety is or has been compromised, the subject may be withdrawn from the study. Subjects may be discontinued from study drug prior to their completion of the study due to any of the following safety criteria being met.

#### 8.5.1.1. Individual Subject Stopping Criteria

Any of the following criteria will be considered as stopping criteria for the study eye in individual subjects:

- An increase from baseline in CMT  $\geq 75 \mu\text{m}$  when seen across two consecutive visits
- A loss of  $\geq 15$ -letters of vision as determined by ETDRS, from the best previous in-study BCVA, due to DME, with current BCVA not better than baseline
- A loss of  $\geq 10$ -letters of vision from best previous in-study BCVA (determined by ETDRS), due to DME, seen across two consecutive visits, with current BCVA score not better than baseline
- Persistent intolerable ocular irritation or redness
- Development of persistent corneal opacities or severe keratitis

- An  $\geq 10\%$  increase in corneal thickness in the study eye based on pachymetry assessed at a consistent time of day
- Intraocular pressure (IOP) increase of 12 mmHg or more (from baseline measurements) confirmed upon repeat testing
- Occurrence of any severe graded AE that is assessed by the Investigator to be related to study drug
- Occurrence of any serious adverse event assessed by the Investigator to be related to study drug
- If a subject's CMT is 420  $\mu\text{m}$  or less, the subject is withdrawn from the study if there is BOTH a loss of BCVA of  $\geq 10$  letters AND an increase in CMT of  $\geq 50 \mu\text{m}$
- If a subject's CMT is  $>420 \mu\text{m}$ , the subject is withdrawn if there was also EITHER a loss of BCVA of  $\geq 10$  letters OR an increase in CMT of  $\geq 50 \mu\text{m}$
- The Investigator believes it is in the best interest of the subject to discontinue study drug dosing and/or initiate an anti-VEGF or other rescue therapy.

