***Stopping Criteria and Dose Holding***

Subjects who do not meet individual subject stopping criteria at the clinical evaluation visits will continue dosing until final day of dosing. Subjects who meet the stopping criteria will be discontinued from dosing but continue to receive safety and efficacy evaluation and all

scheduled clinical assessments as well as follow-up at an EOS Visit 28 days post the subject's last dose where possible.

Detailed stopping criteria for individual subjects and guidance for study Investigators are provided in Section 8.5.1.1. However, these criteria include an increase from baseline in CMT of  $>75 \mu\text{m}$  and a loss of 15-letters of vision. In the case of these two specific stopping criteria being met, at the discretion of the Investigator, rescue medication comprising a marketed anti-VEGF therapeutic will be made available to the patient. The Sponsor would reimburse the cost to the site to a maximum of two doses, or until the drug became approved by the Pharmaceutical Benefit Scheme or other health insurance, whichever occurs first.

The study Investigator in conjunction with the study MM [REDACTED] and also Sponsor's MM may decide to discontinue study drug for an individual subject, based on pre-defined decision rules for reasons of safety. Subjects who discontinue study drug will continue to be followed for safety and efficacy outcomes for the remainder of the study.

Detailed stopping criteria for cohorts are provided in Section 8.5.2. Current cohort doses can be held, and dose escalations planned for the next cohort can be stopped based on cohort stopping criteria, until discussion by the Principal Investigator (PI), DEC, study MM [REDACTED] and also the Sponsor MM has resulted in a decision.

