EXN407 has the potential to be a non-invasive alternative to intravitreal anti-VEGF injections. Subjects with DME who may be unsuitable for or put off by the need for an intravitreal injection may benefit from EXN407 eye drops. It is important to note that subjects who participated in the landmark studies with anti-VEGFs had had DME on average for 1.6 - 2.4 years ([Nguyen 2012](#)). Despite this, approximately 30% of those randomized to receive sham treatment did not need any rescue treatment during the first 6 months of follow-up. Since participants in this study will be identified early, the slight delay caused by the study is not expected to be a significant risk for disease progression. To ensure subject safety, all subjects will be closely monitored and, if any subject shows a clinically significant deterioration in CMT and/or BCVA, they will be withdrawn in a timely manner and offered the standard of care.

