#### **6.4.2. Dose Escalation Cohorts**

##### *Cohort 1*

Once data at the Day 8 time point for the sentinel subjects are reviewed and judged satisfactory by the DEC, all remaining (3) subjects in this cohort can initiate dosing as described previously.

Following completion of all assessments on Day 8 (Visit 5A) for the entirety of cohort 1, the DEC will review safety and tolerability data. Once all applicable data through the Day 8 time point are reviewed and judged satisfactory by the DEC, a recommendation will be made to the Sponsor and documented regarding dose progression/escalation.

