## **8.5.2. Safety Criteria for Suspending or Stopping a Cohort**

### **8.5.2.1. Dose Escalation Cohorts (First in Human)**

Any of the following criteria will be considered as stopping criteria for either stopping a cohort or stopping progression to the next higher dose level:

- The mean  $\text{AUC}_{0-\text{last}}$  from PK plasma results is greater than the max AUC reported in the 13-week topical ocular toxicity study in NHP (Study 57012928) [i.e., 8.04 (hr\*ng)/ml]
- $\geq 50\%$  of subjects within a cohort meet stopping criteria or are withdrawn by the PI (for other than personal or administrative reasons)
- $\geq 1$  Serious adverse event (SAE) which was considered treatment related and occurred while on study drug within 7 days of treatment
- $\geq 2$  AEs which were severe and considered treatment related and which occurred while on study drug within 7 days of treatment

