### **8.5.3. Use of Rescue Medication**

In the case of any of the first two individual subject stopping criteria being met in the study eye, at the discretion of the Investigator, rescue medication comprising a marketed anti-VEGF therapeutic will be made available to the subject for the study eye. The two specific individual subject stopping criteria for rescue medication eligibility are:

- An increase from baseline in CMT  $\geq 75$   $\mu\text{m}$  when seen across two consecutive visits
- A loss of  $\geq 15$ -letters of vision as determined by ETDRS, from the best previous in-study BCVA, due to DME, with current BCVA not better than baseline

The Sponsor will reimburse the cost to the site to a maximum of two doses, or until the drug is funded by the Pharmaceutical Benefits Scheme or the cost is covered by health insurance, whichever occurs first. In such an occurrence, if a subject receives rescue medication, the subject will cease further dosing.

In the non-study eye, treatment (including anti-VEGF administered intravitreally) may be used as per standard of care. Subjects receiving treatment in the non-study eye may remain in the study at the discretion of the study Investigator.

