#### **12.3.3. Visit 4A - Day 4**

Subjects will return to the clinic to be assessed for safety and tolerability of the study drug on Day 4 with a window of  $\pm 1$  day, while still receiving BID dosing. Day 3 and Day 4 should not fall on the same day.

The following procedures will be conducted at the follow-up visit:

- Concomitant medications
- AEs since the last visit
- Ophthalmic Exam/ Ophthalmoscopy
- Tonometry to measure IOP

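### The CMT stopping and rescue criterion is stated two ways, and its two-visit form cannot be met on scheduled scans by the Day 8 escalation review

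*Combined protocol and SAP*

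**What the plan says.** **Synopsis, Stopping Criteria and Dose Holding.** It refers to Section 8.5.1.1 for detail, then says "these criteria include an increase from baseline in CMT of" more than 75 µm, together with a 15-letter loss. Meeting these makes rescue medication available at the Investigator's discretion. No second visit is mentioned.

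**Section 8.5.1.1.** The CMT criterion is a rise of at least 75 µm "when seen across two consecutive visits". A 10-letter loss also needs two consecutive visits. Four other CMT or vision criteria carry no two-visit wording:
- a loss of at least 15 letters;
- CMT of 420 µm or less with both a 10-letter loss and a 50 µm rise;
- CMT above 420 µm with either a 10-letter loss or a 50 µm rise;
- Investigator judgement.

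**Section 8.5.3.** "The two specific individual subject stopping criteria for rescue medication eligibility are" the two-visit CMT rise and the 15-letter loss.

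**Where the criteria are used.** Under Section 8.5.2.1 a cohort or the next dose level can be stopped when at least 50% "of subjects within a cohort meet stopping criteria or are withdrawn by the PI". Under Section 6.4.1 the rest of cohort 1 may start once the DEC has reviewed the sentinel pair's Day 8 data, on condition that no stopping criterion is met. Section 6.4.2 sets the escalation recommendation for cohort 1 at the same point: "Once all applicable data through the Day 8 time point are reviewed and judged satisfactory by the DEC". Later cohorts follow the same one-week pattern.

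**The concern.** The primary objective of this first-in-human study is ocular safety, and the individual stopping criteria feed the rule that holds back the next dose level. Two problems arise.

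First, a site or committee member working from the synopsis and one working from Section 8.5 can classify the same Day 8 scan differently, for stopping and for rescue.

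Second, a criterion that needs two post-baseline scans is applied at a review where the schedule provides one. A count of subjects meeting stopping criteria at that review contains no information from this criterion, and a low count could be read as more reassuring than it is. Section 6.3 says that subjects with clinically significant deterioration in CMT or BCVA "they will be withdrawn in a timely manner and offered the standard of care", which makes the timing of confirmation relevant.

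**Working it through.** The plan gives no numerical operating characteristic for this rule, so there is no figure to reproduce. The check compares the wordings with the schedule.

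**1. Wordings side by side**

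| Place | Threshold | Confirmation | Used for |
|---|---|---|---|
| Synopsis | more than 75 µm | none | stopping and rescue |
| Section 8.5.1.1 | at least 75 µm | two consecutive visits | stopping |
| Section 8.5.3 | at least 75 µm | two consecutive visits | rescue |

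They differ in the sign at exactly 75 µm and, more importantly, in confirmation.

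**2. Escalation schedule (Table 5; Sections 12.3.1 to 12.3.5)**

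- SD-OCT and BCVA: Screening, Day 1, Day 8, Day 36 (±2). Neither is done on Day 3 or Day 4.
- Post-baseline assessments by Day 8: 1. Needed: 2.
- Earliest day on which either two-visit criterion can be met: Day 36.
- Delay after the Day 8 data: 36 − 8 = 28 days (26 to 30 with the window).
- Dosing ends on Day 7. On scheduled scans no CMT criterion, confirmed or not, can stop an escalation subject's own dosing. At Day 8 the criterion matters for the cohort rule, the sentinel condition and rescue eligibility.

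**3. Who falls in the gap at Day 8**

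Take a rise of at least 75 µm and read the 420 µm criterion as current CMT.

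- Baseline b with b + 75 > 420, that is b > 345 µm: the above-420 criterion is met at one visit, so the subject counts.
- Baseline 280 to 345 µm with a 75 µm rise: current CMT is 420 µm or less. The subject counts only with at least 10 letters lost or by Investigator judgement.
- For a larger rise d the upper baseline limit falls to 420 − d. With d = 95 it is 325 µm.

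The gap is therefore a rise of at least 75 µm, current CMT of 420 µm or less and fewer than 10 letters lost. Such a subject meets no objective CMT or BCVA criterion in Section 8.5.1.1 at Day 8, yet meets the synopsis criterion if the rise exceeds 75 µm. If the 420 µm criterion means baseline CMT, it applies to almost no eligible subject (eligibility is 280 to 420 µm) and the gap widens. The text does not say which is meant.

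For rescue under Section 8.5.3, the CMT route needs the second visit whatever the current CMT.

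**4. Effect on the cohort rule**

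The 50% rule needs 3 of 5 subjects in cohort 1 and 2 of 4 in cohorts 2 and 3.

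*Constructed example.* Two of four subjects go from 300 to 395 µm (+95) with BCVA unchanged and no Investigator action. Synopsis: 2/4 = 50%, and the rule is met. Section 8.5.1.1: 0/4 = 0%.

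*Range.* Let p be an assumed chance per subject of a Day 8 rise that meets a single-visit version; the documents give no value. The chance that this version alone trips the rule is P(X ≥ r) with X binomial(n, p):

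| p | 3 of 5 | 2 of 4 |
|---|---|---|
| 0.10 | 0.009 | 0.052 |
| 0.20 | 0.058 | 0.181 |
| 0.30 | 0.163 | 0.348 |

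On scheduled visits the two-visit criterion contributes 0 at Day 8 for every p.

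**5. Expansion (Table 5; Section 12.4)**

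Post-baseline SD-OCT is on Days 8, 29, 57, 85 and 113. Clinic visits are on Days 8, 15, 29, 57, 85 and 113; Day 15 has no scan and Day 22 is a telephone contact. If consecutive means consecutive SD-OCT visits, the first pair is Days 8 and 29. If it means consecutive clinic visits, the first pair is Days 29 and 57. The earliest confirmation is Day 29 or Day 57, and the text does not choose.

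**The case against.** The strongest reply is that the DEC does not decide by the 50% rule alone. It must find the Day 8 data satisfactory, Section 8.4 has it review the available clinical safety data, and the Day 8 visit includes SD-OCT and BCVA. The 15-letter, combined and above-420 criteria can be met at one visit, and Investigator judgement is always open, including to start anti-VEGF therapy. Section 14.1 foresees unscheduled procedures for urgent safety concerns. The synopsis refers to Section 8.5.1.1 for detail. The DEC charter, which is not among the documents, is to define the safety observations that require a dosing decision and may already call for the listing proposed here.

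Most of this stands, and it limits the point. A reader might infer any of the following, and the documents support none of them:

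- *Retinal worsening cannot count at Day 8.* It can, through the other criteria and the DEC's review.
- *The above-420 criterion conflicts with the two-visit criterion.* Section 8.5.1.1 lists alternatives, any one of which suffices. Overlap is not contradiction.
- *In expansion only Days 29 and 57 can confirm a rise in time to stop dosing.* This holds only if Day 15, which has no scan, counts as an intervening visit.
- *About half of subjects are affected, or unaffected.* Baselines above 345 µm are 75/140 = 54% of the eligible range. That is a share of micrometres, not of patients; no CMT distribution is given.

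The reply does not remove the difference between synopsis and body, which is a different condition rather than a shorter statement of the same one. Nor does it make the two-visit criteria operable at Day 8. A repeat scan is possible but not required, and committee discretion is not the pre-specified rule.

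**Conclusion.** The point holds in a limited form. The CMT criterion has two incompatible wordings for stopping and rescue. In escalation, on scheduled visits, the two-visit CMT and 10-letter criteria can first be met about 28 days after the data on which the DEC decides, so they contribute nothing to the cohort rule or the sentinel condition at that review. For the stopping count, the unprotected case is the one defined in step 3. In expansion the meaning of consecutive visits moves the earliest CMT confirmation by 57 − 29 = 28 days.

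This rests on three assumptions: scheduled assessments only; a DEC meeting soon after Day 8 (a late meeting could include subjects who have reached Day 36); and, for the baseline range, the 420 µm criterion read as current CMT. How many subjects would fall in the gap cannot be derived from the documents. Because ocular safety is the primary objective, a contradictory decision threshold should be corrected even though other safeguards exist.

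**What to change.** 1. Reconcile the synopsis, Section 8.5.1.1 and Section 8.5.3 into one wording. The threshold sign and the confirmation rule are clinical decisions for the sponsor's clinicians.
2. Define consecutive visits by the SD-OCT and BCVA assessments in Table 5, separately for escalation and expansion.
3. State whether the 420 µm criterion refers to current or baseline CMT, and how meeting it relates to rescue eligibility under Section 8.5.3.
4. Whichever wording is kept, have the DEC's Day 8 package list each subject's change from baseline in CMT and BCVA and flag anyone at threshold but unconfirmed, before the sentinel and progression recommendations. If the charter already requires this, a cross-reference is enough.

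The cost is an amendment to wording and one listing of data already collected, with no added visits or subjects. The downside is small: some unconfirmed measurement noise will reach the DEC.
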